13.5 Outcome Definitions

The outcome is reported in relationship to the Adverse Event, not the treatment rendered for the event (if any).

13.5.1 Recovered/Resolved

The adverse event has been resolved and/or no further treatment is required to treat the reported condition or illness.

13.5.2 Recovering/Resolving

Treatment or diagnostic studies were prescribed for the adverse event and the outcome of the adverse event is being resolved and patient is recovering, but has not completely recovered.

13.5.3 Not recovered/Not resolved

The adverse event is not yet resolved and the patient has not recovered from the adverse event.

13.5.4 Chronic, clinically stable

The adverse event will most likely never be resolved. The subject “tolerates” the illness or condition as a matter of life.

13.5.5 Death

The outcome indicates the subject died as a direct result of the reported adverse event.

14 Monitoring

Zimmer Knee Creations, Inc., as Sponsor of this clinical investigation, as well as IMARC Research, Inc. will be responsible for monitoring this study. The monitor’s duties are to aid the Clinical Investigator in the production and maintenance of complete, legible, well-organized and easily retrievable data. In addition, the Monitor will be responsible for assuring the Clinical Investigator understands the protocol and all applicable regulations. Approaches to monitoring include both remote and on-site visits as appropriate and the rationale and frequency for monitoring will be at the Sponsor’s discretion.

The Monitor may check the CRF entries with source documents, primarily looking at the Operative Report CRF. In order to perform this role effectively, the Monitor must be given access to primary subject data which supports the information recorded on the CRF, i.e. hospital notes, appointment books, etc. Access to these documents must also be given should the regulatory authority instigate an external audit. Since a subject has the right to refuse access to these documents on the grounds of confidentiality, consent to access is included in

the informed consent document, which the subject signs.

The Clinical Investigator will receive reasonable notification prior to each monitoring visit during the course of this clinical investigation. The monitoring frequency will be determined for each site based on factors including: the planned enrollment, the rate of enrollment, the level of experience of the clinical investigation team and the current study conduct. At each visit, the Clinical Investigator will be expected to cooperate with the Monitor for the review and verification of CRFs and any additional records as may have been previously arranged between the Clinical Investigator and the Monitor. A monitor log will be kept on site for monitor signature upon any visit completed.

This is a post-market study that does not involve investigational products or procedures, and the physical risks to the patients for participation in the study are minimal. Many assessments are standard-of-care for these patient populations and do not require special training for their use in the study. Non-standard assessments, such as patient-reported outcome measures (PROMs), are used frequently in clinical research and instructions can easily be communicated by remote methods. As such, site initiation visits may be conducted remotely for this study.

15 Risk Analysis

This study was designed to assure that the benefits and knowledge gained by studying clinical outcomes associated with Subchondroplasty for treatment of BMLs in the hip outweigh the potential risks to the subjects. Alternative treatment options may require more invasive surgical therapy to treat the painful hip, up to and including arthrodesis or arthroplasty.

15.1 General

Risks of surgical intervention

With any surgical procedure, there are risks of complication including those risks currently associated with surgical interventions in the hip. These risks include intra-articular adhesions (scar tissue), superficial and/or deep wound infection, nausea and/or vomiting, bleeding, hip pain, muscle weakness, and postoperative blood clot (hematoma). There are possibilities of wound re-opening, deep vein thrombosis (blood clot), pulmonary embolus (lung clot), vascular or nerve injury, and an allergic response to the anesthetic or medications. Some additional risks related to local anesthesia are swelling, pain, bleeding, bruising, nerve pain and loss of sensation in the skin and ligament around the hip.

Risks associated with subchondral implantation of AccuFill

Risks specific to the implantation of a bone marrow substitute may include tissue thinning over the implant site, tenderness/redness/edema, seroma/hematoma, infection, swelling/fluid collection and loss of contour. Migration, extrusion, dehiscence, fracture and sloughing of AccuFill can occur as a result of excessive trauma. Neurovascular injury may occur due to surgical trauma. A pulmonary embolism may result from using this injectable bone void filler.

Methods to minimize risk

Only appropriate subjects, who meet the include inclusion and exclusion criteria, will be recruited into the study.

Study subjects will be monitored post-operatively to assess the surgical site for any acute and chronic adverse reactions to ensure proper medical treatment can be administered. Validated and standardized outcome scales and surveys will be used to collect subjects' data. Experienced orthopedic surgeons will participate as investigators and have experienced staff to perform the study procedures.

Benefits and Justification for the Study

This is an observational study and there are no direct benefits to the subject, other than those associated with the treatment of a bone marrow lesion of the hip. The justification for this study is to learn more about patient outcomes following the Subchondroplasty procedure in the hip.

15.2 Indemnification

The indemnification provision is located in the Indemnification section of the executed clinical trial agreement.

16 Statistical Methods

16.1 Sample Size Calculation

The sample size required is based on the overall group mean improvement of the Harris Hip Score by at least the minimal clinically important differences (MCID) of 18.0 points from baseline to one year.

Based on internal Zimmer Biomet studies, assuming an improvement from baseline of 31.4 points with a standard deviation of 22.4, 80% power and alpha set at 0.05, 24 patients are needed to show the mean improvement from baseline is greater than the MCID of 18.0. Considering an attrition rate of 25%, 32 patients should be enrolled in the study. At an enrollment rate of approximately 50 subjects the study is more than adequately powered to show improvement over the MCID.

16.2 General Statistical Methods

Data collected in this study will be summarized descriptively and will be the basis of study reports. Descriptive summaries will be used to generate an overall summary of the clinical performance of the Subchondroplasty Procedure in hip cases and may be used for reports or to support presentations or publications.

16.3 Data Analysis

Summaries will routinely describe categorical data as counts and percentages. Routine summaries describing continuous data will be in the form of means, medians, standard deviations, minima and maxima; ninety-five percent confidence intervals will be used. Routine summaries of return to function, patient outcomes measures, etc. will generally be accompanied with the corresponding crude rates (expressed as percentages). Routine summaries of complication data will be in the form of frequencies and percentages. Summaries may be further

generated for strata within the study population, (e.g., males and females, different cut-points in the body mass index continuum, etc.). Subject confidentiality will be protected at all times and subject identifiers will not be included in study summaries.

17 Quality Control & Quality Assurance

The study is conducted in accordance with the Declaration of Helsinki and the ISO 14155:2020.

The Investigator will be required to permit representative(s) of the Sponsor's monitoring team to inspect all Case Report Forms and corresponding sections of the study patients office records and/or hospital original medical records. These audits will be done for quality assurance purposes, i.e. verifying adherence to the Clinical Investigation Plan and the completeness and accuracy of the data being entered on the Case Report Forms.

The Clinical Investigation Plan will be provided to all participating study centers. The Investigators will be fully trained in the proper reporting and submission of trial data prior to patient enrolment. Completed Case Report Forms will be reviewed before entering the data into a central database by the Sponsor.

The Clinical Study Manager is responsible for generating data queries for missing or unclear data if needed. It is the responsibility of the Clinical Study Manager to ensure data quality.

There are regular meetings between the Investigators and Zimmer Biomet Clinical Affairs staff. Written correspondence to all sites is used to inform the Investigators of routine study details and to update them on study status.

18 Suspension or Premature Termination of the Clinical Investigation

Zimmer Biomet may decide to suspend or prematurely terminate the clinical study at one or more investigational sites for significant and documented reasons, such as information becomes available that the risk to study subjects is higher than initially indicated.

In the case of an early termination of the study, the IRB/EC and regulatory authority(ies) should be informed in accordance with regional and/or national laws/regulations, and IRB/EC requirements. The reasons for termination should be provided and documented.

- Further follow-up of the study subjects shall proceed according to the investigator's standard of care or hospital's standard procedures.

19 Vulnerable Populations

No vulnerable patients will be included in the study.

20 Amendments / Modifications to the Clinical Investigation Plan

Any proposed amendments to this protocol must be submitted in writing and pre-approved by the Sponsor. All Sponsor-initiated protocol amendments will be documented in writing, including the date and justification for the change, and communicated in a timely manner to the

Investigators. All amendments are to be approved by the reviewing IRB prior to implementation.

21 Publication Policy

Institution or Investigators may publish, present, or use any results arising out of the performance of this Study for its or their own publication, presentation, instructional, or non-commercial research objectives provided that the publication, presentation, or use does not disclose any Confidential Information furnished by Sponsor, occurs only after completion of the Study, and contains only final Study data and analysis, unless otherwise approved by Sponsor.

Institution and each Investigator agrees that any proposed publication or presentation relating to the Study conducted under this Agreement will be submitted to Sponsor for review (not for approval or disapproval) at least thirty (30) days prior to submission for publication or presentation. In the event that the proposed publication or presentation contains patentable subject matter that needs protection, Institution and Investigators will, upon request received from Sponsor within the thirty (30) day review period, delay the publication or presentation for an additional ninety (90) days to allow Sponsor to file a patent application. Sponsor will have the right to require deletion of any Confidential Information or other proprietary information belonging to the Sponsor or information identifying Qualified Participants in the Study, unless otherwise required by law.

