10.7.1 Primary Endpoint

The primary endpoint is defined by the overall group mean improvement from baseline of the Modified Harris Hip Score at the two year time point. The safety of the system will be assessed by monitoring the frequency and incidence of adverse events. Relation of the events to implant (Accufill®), instrumentation (SCP® Surgical Instrumentation) and/or procedure should be specified.

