11.8 Minimization of Loss to Follow-up

Subject follow-up is extremely important for the conduct of a clinical study. The expectation is to maintain the highest rate of follow-up compliance possible throughout this study. Subjects that are study completed as lost to follow-up will not be replaced. In an effort to minimize the number of subjects lost to follow-up, the following recommendations and/or study requirements are essential to ensure proper patient selection and compliance:

- Patient Eligibility: Subjects will be selected according to the inclusion/exclusion criteria detailed in Section 8 and are expected to return for all follow-up visits.
- Patients Counseled: Patients will be counseled during the Informed Consent process on the importance of returning for follow-up visits.
- Patient Exclusion: Patients who are not willing to return for study required follow-up visits and/or are not willing to comply with the follow-up schedule will not be considered for enrollment into the study.
- Subject Due Listings: In addition to proper patient selection, Zimmer Biomet will provide subject due notices to the sites on a regular basis in order to track each study participant and monitor adherence to the required follow-up visit timeframes. The subject due listings will facilitate scheduling the subjects for their return office visits.
- Contact Tracking: Attempts to contact subjects will be documented in the study subject's medical record. It is recommended that the first three attempts be made by telephone. If after three calls, contact has not been successful, the below is suggested prior to terminating the study subject from the study:

If	Then
a response is not received following attempts to reach the subject by phone	the Investigator could send a letter to the patient explaining the follow-up agreement per informed consent.
a response is not received from the Investigator's letter	the Investigator could use any additional contacts provided by the subject to contact the subject.
The subject missed three consecutive visits and all attempts to contact the subject are unsuccessful, or the subject is contacted and chooses to withdraw from the study	the Study Completion form may be completed and will specify the reason the patient is no longer participating in this study.

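### The primary two-year mean can use only subjects with a two-year score and leaves the interim Modified Harris Hip Scores unused, so selective loss to follow-up can bias it, probably upward

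*Combined protocol and SAP*

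**What the plan says.** Section 10.7.1 defines the primary endpoint as the "overall group mean improvement from baseline of the Modified Harris Hip Score at the two year time point". Sections 16.2 and 16.3 hold the whole analysis plan, and for continuous outcomes it reads "Routine summaries describing continuous data will be in the form of means, medians, standard deviations, minima and maxima", with 95% confidence intervals. There is no analysis set, missing-data rule, longitudinal model or sensitivity analysis.

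On losses, section 16.1 says "Considering an attrition rate of 25%, 32 patients should be enrolled in the study", and section 11.8 says "Subjects that are study completed as lost to follow-up will not be replaced". The section 16.1 calculation is framed as a "minimal clinically important differences (MCID) of 18.0 points from baseline to one year", so its allowance is worded to one year while the endpoint is at two. It is not divided between surgical exits and other loss.

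Table 1 and section 11.7 schedule the Modified Harris Hip Score at 6 weeks, 12 weeks, 6 months, 1 year and 2 years. The synopsis row on materials and methods and section 10.6 carry shorter visit lists. Section 12.4.4 keeps data gathered before withdrawal in the database unless the subject asks otherwise in writing, but does not say how they enter the primary estimate. Section 11.4 accepts a pre-operative score for subjects enrolled after surgery only if it was obtained in routine care.

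**The concern.** The endpoint is a mean for the whole group. With no imputation or model named, the analysis the text supports is the mean of observed two-year changes. That equals the group mean only if loss is unrelated to outcome.

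Non-response is a realistic route to loss. Follow-up needs no office visit (section 11.7), investigators may withdraw subjects who do not keep to the questionnaire schedule (section 12.4.4), and unanswered contacts lead to lost-to-follow-up status (section 12.4.5). If worse-scoring subjects are likelier to go silent, the reported improvement is too high and its interval covers the true mean less often than stated. There is no control arm in which similar losses might offset the error. Scores that could reduce it are already scheduled.

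**Working it through.** **Reproducing the plan's figures (section 16.1).** Inputs: "assuming an improvement from baseline of 31.4 points with a standard deviation of 22.4"; threshold 18.0; "80% power and alpha set at 0.05, 24 patients are needed".
- Effect tested: 31.4 − 18.0 = 13.4, SD 22.4.
- One-sample t-test, two-sided 0.05, noncentral t: n = 24, power 80.1%. This matches.
- Attrition: 24 / (1 − 0.25) = 32. This matches.
- With 50 enrolled and 25% lost, 50 × 0.75 = 37.5 have a two-year score. Power is about 94–95%, so lost power is not the issue.

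**Bias identity.** With a fraction f lost, bias of the observed mean = f × (mean of completers − mean of those lost). Taking completers at 31.4 and f = 0.25:
- those lost average 31.4: 0.25 × 0 = 0
- those lost average 18: 0.25 × 13.4 = +3.35 (all-subject mean 28.05)
- those lost average 0: 0.25 × 31.4 = +7.85 (all-subject mean 23.55)
- all-subject mean falls to 18 only if those lost average (18 − 0.75 × 31.4) / 0.25 = −22.2

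The documents give no scores for lost subjects, so these are bounds for orientation.

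**Simulation.** From the plan: mean 31.4, SD 22.4, n = 50. Assumed: correlation of 1-year with 2-year change 0.5 to 0.8; odds of loss 1.5 to 3 times higher per SD worse 1-year change; loss after year 1, depending only on the 1-year change. The comparison is the observed mean against a regression estimate that uses the 1-year change.

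| Non-surgical loss | Bias of observed mean | Coverage of 95% interval |
|---|---|---|
| 10–15% (assumed) | +0.5 to +2.6 | 95% to 88% |
| 25% (whole allowance) | about +1 to +4 | 94% to about 79% |

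In the central case (correlation 0.7, odds ratio 2), the bias is +2.5 with 90% coverage at 25% loss, and +1.0 to +1.6 with 93–94% coverage at 10–15% loss.

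Using the 1-year change brings the bias below 0.1 point throughout. At 25% loss its standard error is slightly smaller in the central case (3.44 against 3.57) and marginally larger only at correlation 0.5 with odds ratio 3 (3.64 against 3.59).

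**If the true mean were exactly 18.** With 25% loss, correlation 0.3 to 0.7 and odds ratio 2 to 4 (assumed), the chance that the lower limit exceeds 18 rises from 2.5% to between 5% and 21%.

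**Limit of the correction.** If only a 12-week score is available and loss tracks unobserved 1-year status (assumed correlations 0.4 to 0.6), adjustment cuts the bias only from +2.4 to +1.4, or from +4.1 to +3.2.

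**The case against.** - **The 25% figure.** A reader might infer that a quarter of subjects are planned to have no two-year score. The documents do not say so. The 25% takes 24 to 32 in a one-year calculation, and two-year loss could be lower or higher. Sections 11.7 and 11.8 describe due listings, repeated contact and several response routes. This stands.
- **Surgical exits.** The allowance may include conversions and revisions, which sections 10.4, 11.9 and 12.4.4 take out of the study. Assigning all of it to non-response gives the upper end of the range. This stands, and is why the 10–15% row is shown.
- **Best-case test of the remedy.** The near-zero residual bias follows from letting loss depend only on an observed 1-year score. The check was a two-visit regression, not the full five-visit model. Under the route suggested in section 11.8, a subject who misses 6 months, 1 year and 2 years has nothing after 12 weeks. This stands, so a sensitivity analysis is needed beside the model.
- **Limited consequence.** At a true mean of 31.4 the lower limit exceeds 18 in about 97% or more of the simulated studies with selective loss, and the study is descriptive. That is true of the comparison with 18. It does not protect the estimate and interval, which section 16.2 says may support publications.
- **Silence is not commitment.** Section 16.3 does not expressly prescribe a completers' analysis. That is correct, but it names nothing else, and a mean two-year change cannot include a subject without a two-year score.

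**Conclusion.** The point holds as a risk. The only stated analysis of the primary endpoint can use only subjects with a two-year score, and it leaves scheduled interim scores unused. If loss is related to poor outcome, the result can be biased, probably upward. The illustrative size is about +0.5 to +2.6 points at 10–15% non-surgical loss, and about +1 to +4 points with coverage down to about 79% if the full 25% is non-surgical. Both ranges rest on the assumed correlation, odds ratio and timing of loss.

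Two stronger conclusions are not supported. One is that the primary result is biased by a known amount: the documents say nothing about how lost subjects differ from completers. The other is that a mixed model would remove the bias: it corrects only for loss explained by observed scores.

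**What to change.** In section 16.3:

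1. Make the primary estimate the two-year mean change from a repeated-measures mixed model (visit as a factor, baseline score, unstructured covariance) over all post-operative Modified Harris Hip Scores, with its 95% confidence interval. Include implanted subjects with a baseline score and at least one post-operative score.
2. Report how many subjects lack a baseline score and how many lack a two-year score. Some subjects enrolled after surgery may have no baseline (section 11.4).
3. Keep the observed mean as a supporting summary.
4. Add a sensitivity analysis that lowers missing two-year changes by 5, 10 and 15 points.
5. State a separate analysis rule for subjects exited at conversion or revision. Without one, the model would silently predict their scores as if the procedure had not occurred.

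The shorter visit lists in the synopsis and section 10.6 should be reconciled with Table 1, because the model depends on the interim visits.

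The cost is SAP wording and a standard model fit, with no extra patients, visits or data. The headline improvement may come out slightly smaller, and the standard error may be marginally larger when correlation is low and loss strongly selective.

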23 Appendices

- A. Case Report Forms
- B. Study Logs
- C. Sample Informed Consent
- D. Package inserts
